2.1.2. Relative Day by Study Phase

An analysis relative day (ADY) will be calculated for all assessments at all visits for each participant by study phase.

2.1.2.1. Double Blind Relative Day

Double Blind (DB) start date (DB Day 1) is defined as the date of first study intervention intake. If the date of the first study treatment administration differs among the treatments (e.g. JNJ-3989, JNJ-6379, or NA), the earliest administration date/time is used. All efficacy and safety assessments during the double-blind phase will be assigned an analysis study day relative to this date.

The DB study day in the double-blind treatment phase (ADY) is defined as:

$$DB\ ADY = visit\ date - DB\ start\ date + 1$$

for visits on or after DB Day 1, and

$$DB\ ADY = visit\ date - DB\ start\ date$$

for visits before DB Day 1 (Screening phase).

There is no 'DB Day 0'.

2.1.2.2. Follow Up Relative Day

Follow Up (FU) start date (FU Day 1) is defined in [Table 1](#). All efficacy and safety assessments during the FU phase will be assigned a day relative to this date. The FU study day in the FU treatment phase (ADY) is defined as:

$$FU\ ADY = visit\ date - FU\ start\ date + 1$$

2.1.2.3. Extended Follow Up Relative Day

Extended Follow Up (EFU) start date (EFU Day 1) is defined in [Table 1](#). All efficacy and safety assessments during the extended FU phase will be assigned a day relative to this date. The EFU study day in the extended FU treatment phase (ADY) is defined as:

$$EFU\ ADY = visit\ date - EFU\ start\ date + 1$$

2.1.3. Analysis Visits and Time Points

All visits for all assessments (safety, efficacy or PK) will be uniquely allocated within each phase to an analysis time point based on the analysis relative day (ADY) compared with the target day based on [Table 2](#). All assignments will be made in chronological order. Once a visit is assigned to a visit window (Time interval in [Table 2](#)), it will no longer be used for a later time point except for the end of treatment (EOT) and the end of study (EOS) visits. If two or more visits fall within the same interval in the same phase, only one measurement will be selected for the analysis time point per phase in order to have only one evaluation per participant. The following rules will be applied:

1. The measurement closest to the target day in that phase will be used.
2. If the measurements fall equidistant from the target day, the last measurement in chronological order within the interval will be used per phase
3. If there are two or more measurements on the same day, then the last measurement in chronological order will be used. If the time of the assessment is not available the highest record/sequence number will be selected.

The listings will include all measurements, also those multiple assessments within the same visit window/phase.

End of treatment (i.e. EOT) and end of study (i.e. EOS) time points will be included in all analysis over time unless stated otherwise.

Note: For the selection of the patient-reported outcome (PRO) measurements the above algorithm needs to be performed on the entire questionnaire (filled in at a specific date and time) and not on the individual questions /items (i.e., not mixing answers from different questionnaires)

Table 2 provides the analysis time points, time intervals for each visit per analysis phase.

Table 2: Analysis Time Points and Time Intervals by Analysis Phase

a) **Screening and Double-Blind Phases**

Analysis phase	Target day	Analysis time point (Week)	Analysis time point (label)	Time interval (days)
Screening	$-\infty$	-1	Screening	<0
Double-Blind	1	0	Baseline	Pre-dose
	8	1	Week 1	[2,11]
	15	2	Week 2	[12,22]
	29	4	Week 4	[23,36]
	43	6	Week 6	[37,50]
	57	8	Week 8	[51, 71]
	85	12	Week 12	[72, 99]
	113	16	Week 16	[100, 127]
	141	20	Week 20	[128, 155]
	169	24	Week 24	[156, 183]
	197	28	Week 28	[184, 211]
	225	32	Week 32	[212, 239]
	253	36	Week 36	[240, 267]
	281	40	Week 40	[268, 295]
	309	44	Week 44	[296, 323]
	337	48	Week 48	[324,350]
	last visit in double-blind phase	49 ^a	EOT ^a	

^a End of treatment (EOT) visit will be the last post-baseline visit in double-blind phase.

b) **Follow-Up Phase**

Analysis phase (FU)	Target day	Analysis time point (Week)	Analysis time point (label)	Time interval (days) ^a (Arm 1-5 and Arm 6 [NA stopped])	Time interval (days) ^a (Arm 6 [NA continued])
Follow-up ^a	15	50	Follow-up Week 2	[1, 22]	
	29	52	Follow-up Week 4	[23,36]	
	43	54	Follow-up Week 6	[37,50]	
	57	56	Follow-up Week 8	[51, 71]	
	85	60	Follow-up Week 12	[72, 99]	[1, 99]
	113	64	Follow-up Week 16	[100, 127]	
	141	68	Follow-up Week 20	[128, 155]	
	169	72	Follow-up Week 24	[156, 190]	[100, 190]
	197	76	Follow-up Week 28	[191, 204]	
	211	78	Follow-up Week 30	[205, 218]	
	225	80	Follow-up Week 32	[219, 232]	
	253	84	Follow-up Week 36	[233, 274]	[191, 274]
	281	88	Follow-up Week 40	[275, 288]	
	295	90	Follow-up Week 42	[289, 302]	
	309	92	Follow-up Week 44	[303, 316]	
	337	96	Follow-up Week 48	[317, $+\infty$]	[275, $+\infty$]

c) Extended Follow-Up Phase

Analysis phase (EFU)	Target day	Analysis time point (Week)	Analysis time point (label)	Time interval (days) ^a
Extended Follow-up	15	102	Ext Follow-up Week 2	[1, 22]
	29	104	Ext Follow-up Week 4	[23, 36]
	43	106	Ext Follow-up Week 6	[37, 50]
	57	108	Ext Follow-up Week 8	[51, 71]
	85	112	Ext Follow-up Week 12	[72, 99]
	113	116	Ext Follow-up Week 16	[100, 127]
	141	120	Ext Follow-up Week 20	[128, 155]
	169	124	Ext Follow-up Week 24	[156, 190]
	197	128	Ext Follow-up Week 28	[191, 204]
	211	130	Ext Follow-up Week 30	[205, 218]
	225	132	Ext Follow-up Week 32	[219, 232]
	253	136	Ext Follow-up Week 36	[233, 274]
	281	140	Ext Follow-up Week 40	[275, 288]
	295	142	Ext Follow-up Week 42	[289, 302]
	309	144	Ext Follow-up Week 44	[303, 316]
	337	148	Ext Follow-up Week 48	[317, +∞]
	last visit in the study	999 ^a	EOS ^a	

^a End of study (EOS) visit (last available data during the extended follow-up) will be the last visit in the study.

2.2. Baseline

In general, the baseline assessment is defined as the last observed non-missing measurement before the date and time of the first administration of any of study treatments.

In case the first administration time is missing, the first observed measurement on DB Day 1 will be used as the baseline measurement. If no observed measurement on DB Day 1, the last observed measurement before DB Day 1 will be used as the baseline assessment.

2.3. Analysis Sets

All randomized analysis set: All participants who were randomized in the study. Participants will be analyzed according to the study intervention they were randomly assigned to.

Intent-to-Treat analysis set (ITT): All participants who are randomized and received at least one dose of any of the study treatments. Participants will be analyzed according to the study intervention they were randomly assigned to.

Modified Intent-to-Treat analysis set (mITT): All participants who were randomized in the study and received at least one dose of study treatment excluding those participants impacted by the pandemic defined as those participants who, because of COVID-19 or similar pandemics related reasons, withdrew prematurely from the study prior to Week 44, or had no efficacy assessment for the primary endpoint. COVID-19 or similar pandemics related reasons may include for example missed visits due to travel restriction, shortage of lab kits at the planned visit, missed collection of blood sample at key time points for the primary efficacy endpoint, etc. Participants will be analyzed according to the study intervention they were randomly assigned to.

Safety analysis set: All participants who received at least one dose of any of the study treatments. Participants will be analyzed according to the study intervention they actually received.

Per protocol analysis set 1 (PP1): All participants in the ITT analysis set who do **not** have any of the selected major protocol deviations that may affect the assessment of efficacy in terms of the primary endpoint at Week 48. The selected major protocol deviations for efficacy analysis purposes that will be used to identify the participants included in the PP set are described in Section 4.5 and [ATTACHMENT 1](#) (column **PP1**). Participants will be analyzed according to the study intervention they were randomly assigned to.

Per protocol analysis set 2 (PP2): All participants in the ITT analysis set who do **not** have any of the selected major protocol deviations that may affect the assessment of efficacy in terms of the key secondary endpoint at Week 72. The selected major protocol deviations for efficacy analysis purposes that will be used to identify the participants included in the PP set are described in Section 4.5 and [ATTACHMENT 1](#) (column **PP2**). Participants will be analyzed according to the study intervention they were randomly assigned to.

Pharmacokinetics analysis set (PK): The PK analysis set is defined as subjects who have received at least 1 dose of any of the study treatments and have at least 1 valid blood sample drawn for PK analysis.

2.4. Definition of Subgroups

The following demographic and screening/baseline characteristics will be used to define subgroups of interest for efficacy analyses (primary endpoint and key secondary endpoint) and selected safety analyses (see Sections [6.1.2](#) and [6.2.2](#)).

2.4.1. Subgroups for Efficacy Analyses

- Sex: Male, Female
- Age categories: ≤ 45 years, > 45 years
- Race: Asian, non-Asian
- Geographical region: Asia, Europe, North America, South America
- Has never received HBV treatment (only currently not treated):
 - Yes
 - No
- Type of NA at study entry (only for virologically suppressed participants):
 - Tenofovir Disoproxil Fumarate (TDF)
 - Tenofovir Alafenamide Fumarate (TAF)
 - Entecavir (ETV)
- Hepatitis B e Antigen (HBeAg) status at screening (qualitative):
 - Positive

- Negative
- Treatment history:
 - Currently not being treated
 - Virologically suppressed
- HBsAg level at baseline:
 - <1,000 IU/mL
 - ≥1,000 IU/mL-<10,000 IU/mL
 - ≥10,000 IU/mL
- HBV DNA level at baseline (only for currently not treated):
 - <100,000 IU/mL
 - ≥100,000 IU/mL
- HBV RNA level at baseline:
 - < 1,000 copies /mL
 - ≥1,000-<10,000 copies /mL
 - ≥10,000 copies /mL
- HBcrAg level at baseline:
 - <3 log U/mL
 - ≥3 log U/mL-<4 log U/mL
 - ≥4 log U/mL
- HBsAg Antibody (Anti-HBs) level at baseline:
 - <10 mIU/mL
 - ≥10 mIU/mL
- Alanine Transferase (ALT) at baseline: ≤ 1.0 ULN, > 1.0 ULN - <2.5 ULN, ≥ 2.5 ULN
- HBV genotype assessed at screening and tested using the INNO-LiPA or sequence based HBV genotyping data: Genotype A, B, C, D, E, F, G, H, I, J and Unknown
- Combination of HBeAg status at screening and treatment history:
 - Positive/Currently not being treated
 - Positive/Virologically suppressed
 - Negative/Currently not being treated
 - Negative/Virologically suppressed
- Combination of HBeAg status at screening and age categories:
 - Positive/≤ 45 years
 - Positive/> 45 years
 - Negative/≤ 45 years

- Negative/> 45 years
- Combination of HBeAg status at screening and HBsAg level at baseline:
 - Positive/<1,000 IU/mL
 - Positive/ \geq 1,000 IU/mL-<10,000 IU/mL
 - Positive/ \geq 10,000 IU/mL
 - Negative/<1,000 IU/mL
 - Negative \geq 1,000 IU/mL-<10,000 IU/mL
 - Negative \geq 10,000 IU/mL
- Combination of treatment history and age categories:
 - Currently not being treated \leq 45 years
 - Currently not being treated $>$ 45 years
 - Virologically suppressed \leq 45 years
 - Virologically suppressed $>$ 45 years
- Combination of treatment history and HBsAg level at baseline:
 - Currently not being treated <1,000 IU/mL
 - Currently not being treated \geq 1,000 IU/mL-<10,000 IU/mL
 - Currently not being treated \geq 10,000 IU/mL
 - Virologically suppressed <1,000 IU/mL
 - Virologically suppressed \geq 1,000 IU/mL-<10,000 IU/mL
 - Virologically suppressed \geq 10,000 IU/mL

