- g. Minimum criteria for the availability of documentation supporting the eligibility criteria are described in the Source Documents section of Section 10.3, Appendix 3, Regulatory, Ethical, and Study Oversight Considerations. Check clinical status (including in- and exclusion criteria) again before first dose of study intervention. If a participant's clinical status changes (including any available laboratory results or receipt of additional medical records) after screening but before the first dose of study intervention is given such that he or she no longer meets all eligibility criteria, then the participant should be excluded from participation in the study.
- h. Medical history also includes mode of HBV transmission and stage of liver fibrosis. Historical HBV DNA, HBsAg, HBeAg, and ALT data, if available, will be recorded in the CRF.
- i. Liver disease staging assessments will be performed based on Fibroscan or liver biopsy results, obtained within 6 months (in case of Fibroscan) or within 1 year (in case of liver biopsy) prior to screening or at the time of screening.

- j. Participants must have absence of signs of HCC or clinically relevant renal abnormalities on an abdominal ultrasound performed within 6 months prior to screening or at the time of screening. In case of suspicious findings on conventional ultrasound the participant may still be eligible if HCC or clinically relevant renal abnormalities have been ruled out by a more specific imaging procedure (contrast enhanced ultrasound, CT or MRI).
- k. HBV genotype will be determined at baseline using standard genotyping assay if HBV DNA levels are sufficiently high. For participants with low HBV DNA levels, available historical data on previous HBV genotype assessment will be collected in the CRF. Exploratory genotyping assays might be performed.
- l. For postmenopausal women only: an FSH level in the postmenopausal range may be used to confirm a postmenopausal state in women not using hormonal contraception or hormonal replacement therapy. However, in the absence of 12 months of amenorrhea, a single FSH measurement is insufficient to confirm a woman is not of childbearing potential.

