5.1. Inclusion Criteria

Each potential participant must satisfy all of the following criteria to be enrolled in the study:

- 1. Adult male or female participants 18 (or the legal age of consent in the jurisdiction in which the study is taking place) to 65 years of age, inclusive.
- 2. Participants must be medically stable, with the exception of HBV disease, on the basis of physical examination, medical history, vital signs, and 12-lead ECG performed at screening. If there are abnormalities, they must be consistent with the underlying illness in the study population. This determination must be recorded in the participant's source documents and initialed by the investigator.
- 3. Participants must have chronic HBV infection documented by serum HBsAg positivity at screening. In addition, chronicity must be documented by serum HBsAg positivity at least 6 months prior to screening or alternative markers of chronicity (HBeAg positivity or HBV DNA positivity at least 6 months prior to screening, ALT elevation above ULN at least 6 months prior to screening without another cause than HBV infection, liver

biopsy, or documented transmission event at least 6 months prior to screening).

Note: if documentation of chronicity (as mentioned above) at least 6 months prior to screening is not available, participants may be included if HBsAg positive and negative for immunoglobulin M (IgM) antibodies to HBc antigen at screening.

- 4. Participants who are **not currently treated** (defined as not having been on HBV treatment, including NAs and IFN products within 6 months prior to screening), including **treatment-naïve** participants (defined as never having received HBV treatment, including NAs and IFN products) should have:
 - a. Serum HBV DNA at screening ≥2,000 IU/mL for HBeAg-negative participants and ≥20,000 IU/mL for HBeAg-positive participants, AND
 - b. ALT levels at screening <10x ULN AND >ULN on two measurements at least 3 months apart (one of which is at screening).
- 5. Virologically suppressed participants should:
 - a. be on stable HBV treatment, defined as currently receiving NA treatment (ETV, TDF, or TAF) for at least 6 months prior to screening and having been on the same NA treatment regimen (at the same dose) as used in this study (see Section 6.1) for at least 3 months at the time of screening, AND
 - b. have serum HBV DNA <60 IU/mL on two measurements at least 6 months apart (one of which is at screening), AND

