8.1.1. Sequencing

Viral genome sequence analysis will be performed to identify pre-existing baseline polymorphisms and to evaluate emergence of mutations associated with JNJ-3989, JNJ-6379, and/or NA treatment.

Sequencing of the HBV genome will be performed to monitor HBV variants present at the time points indicated in the Schedule of Activities. Samples at baseline will be sequenced by default if HBV DNA levels are within the ranges required for the sequencing assay. The sequencing of samples after baseline may be triggered by the sponsor virologist based on changes in HBV DNA levels observed in each individual participant and the limits of the sequencing assay.

Samples may be used by the sponsor for additional assessments analyzing the serologic and virologic characteristics of HBV infection and efficacy and safety of the study intervention, including viral genotypic and phenotypic assessments.

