- HBcrAg category at baseline (quantitative: log U/mL):
 - Participants with HBcrAg <3 log U/mL
 - Participants with HBcrAg \geq 3 log U/mL-<4 log U/mL
 - Participants with HBcrAg \geq 4 log U/mL
- HBsAg Antibody (Anti-HBs) status at baseline (qualitative): Positive, Negative
- HBsAg Antibody (Anti-HBs) at baseline (quantitative): values in mIU/mL and log10 mIU/mL
- HBsAg Antibody (Anti-HBs) category at baseline (quantitative: mIU/mL):
 - Participants with Anti-HBs<10 mIU/mL
 - Participants with Anti-HBs \geq 10 mIU/mL
- HBeAg Antibody (Anti-HBe) status at baseline (qualitative): Positive, Negative
- Alanine Transferase (ALT) at baseline:
 - Baseline ALT values (U/L)
 - Baseline ALT toxicity grade according to DAIDS
 - Baseline ALT categorization (\leq 1.0 ULN, > 1.0 ULN to <2.5 ULN, \geq 2.5 ULN)
- Fibroscan score at baseline (quantitative: kPa)
- Fibrosis Stage: F0, F1, or F2
- HBV genotype (using the INNO-LiPA or sequence based HBV genotyping data): Genotype A, B, C, D, E, F, G, H, I, J, and Unknown

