7.6. HBV genotype

Plasma samples for HBV genotyping were taken at screening and tested using the INNO-LiPA HBV genotyping assay. In addition, plasma samples were taken at baseline to determine the HBV genotype using the HBV full genome sequence and phylogenetic analysis.

The number and percentage of subjects by HBV genotype for study analysis will be tabulated. In addition, cross-tabulations per HBV genotype will compare the HBV genotypes determined by the INNO-LiPA HBV genotyping assay and by using the HBV full genome sequence.

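### The SAP defines HBV genotype from assay or sequence data only and gives no role to the historical genotype the protocol collects, so missing genotypes are likely to concentrate in virologically suppressed participants

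*SAP*

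**What the plan says.** Three SAP sections define the genotype variable, all from the same sources.

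- SAP 2.4.1 (efficacy subgroups): "HBV genotype assessed at screening and tested using the INNO-LiPA or sequence based HBV genotyping data", with genotypes A to J and an Unknown category.
- SAP 4.2.2 (baseline characteristics): "HBV genotype (using the INNO-LiPA or sequence based HBV genotyping data", with the same categories.
- SAP 7.6: "Plasma samples for HBV genotyping were taken at screening and tested using the INNO-LiPA HBV genotyping assay". It adds a baseline sample for full-genome sequencing and a cross-tabulation of the two methods, but does not say which prevails when they disagree.

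The protocol foresees that typing may fail. Footnote k of the schedule in section 1.3.1 says "HBV genotype will be determined at baseline using standard genotyping assay if HBV DNA levels are sufficiently high", and then: "For participants with low HBV DNA levels, available historical data on previous HBV genotype assessment will be collected in the CRF". It adds that "Exploratory genotyping assays might be performed". Sequencing has a similar condition in protocol 8.1.1: "Samples at baseline will be sequenced by default if HBV DNA levels are within the ranges required for the sequencing assay". Neither document gives a numerical HBV DNA threshold for either method.

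Under protocol 5.1, criterion 5b, virologically suppressed participants must "have serum HBV DNA <60 IU/mL on two measurements at least 6 months apart". Under criterion 4a, participants not currently treated need at least 2,000 IU/mL (HBeAg-negative) or 20,000 IU/mL (HBeAg-positive). Protocol 4.1 aims for 40% not currently treated.

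Genotype is an example factor in an exploratory objective (protocol section 3; SAP 1.1) and a subgroup variable for the primary and key secondary endpoints (SAP 2.4, 5.2.5 and 5.3.6).

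**The concern.** The protocol identifies a group whose genotype may not be measurable in the trial and collects a substitute for it. The SAP's derivation does not use the substitute. Followed as written, a suppressed participant with a documented genotype in the CRF but no usable assay or sequence result is classed as Unknown.

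The two treatment-history strata are separated by HBV DNA at entry, so failure to type should follow a randomisation stratum and not be spread evenly over the trial. This has two consequences. Results for the named genotypes may rest mainly on untreated participants. And the contrast between Unknown and the named genotypes may in part be a contrast between suppressed and untreated participants.

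**Working it through.** The plan states no typing rate or expected percentage Unknown, so there is no figure to reproduce. The check is how the result depends on the missing rate.

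**Inputs**

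- Planned N = 450 (protocol 4.1). SAP 1.4 adds about 5%, giving about 472.
- Not currently treated: 40%, an aim and not a fixed quota (protocol 4.1). Suppressed: 60%.
- f = share of suppressed participants typed by INNO-LiPA or sequencing. Not given; assumed, 0% to 80% shown.
- h = share of untyped suppressed participants with a usable historical genotype. Not given; assumed.
- All untreated participants typed; varied below.

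**Numbers by stratum.** Suppressed: 0.60 × 450 = 270. Untreated: 0.40 × 450 = 180. Suppressed per arm: 0.60 × 90 = 54 in Arms 1 to 4, and 0.60 × 45 = 27 in Arms 5 and 6. With N = 472 the totals are about 283 and 189, and the percentages below do not change.

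**Effect of the SAP rule.** Unknown = 0.60 × (1 − f). Untreated share of those typed = 0.40 / (0.40 + 0.60f).

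| f | Unknown, % of trial | Unknown, n of 450 | Untreated share of typed |
|---|---|---|---|
| 0% | 60% | 270 | 100% |
| 20% | 48% | 216 | 77% |
| 50% | 30% | 135 | 57% |
| 80% | 12% | 54 | 45% |

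Most suppressed participants are Unknown only if f is below 50%. The typed group is mainly untreated only if 0.60f < 0.40, that is, f below 66.7%. If only 90% of untreated participants are typed, Unknown becomes 64%, 52%, 34% and 16% in the four rows, and the second break-even moves to 0.36 / 0.60 = 60%.

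**Effect of adding the historical genotype.** Unknown = 0.60 × (1 − f) × (1 − h). With f = 0, h of 25%, 50% and 75% gives 45%, 30% and 15%. With f = 20%, it gives 36%, 24% and 12%.

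**The subgroup model.** SAP 5.2.5 has two parts. The first model is for the stratification factors and includes arm-by-treatment-history and arm-by-HBeAg terms. The second is fitted for each other subgroup variable in turn: arm, treatment history, HBeAg status and the subgroup variable as main effects, and arm-by-subgroup as the only interaction. SAP 5.3.6 uses the same approach for functional cure. Genotype falls under the second. If Unknown lies largely within the suppressed stratum and an arm's effect differs by treatment history, part of that difference can load on arm-by-genotype. The main effect of treatment history does not absorb it.

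**The case against.** **The size is not in the documents.** This stands. A reader might infer that most suppressed participants become Unknown and that the genotype subgroups describe mainly untreated participants. Those statements need f below 50% and below 66.7%, and the documents give neither a typing threshold nor a rate. They support the direction: footnote k ties typing to HBV DNA, and protocol 2.2.1 reports that most suppressed participants in the earlier Phase 2a study were below the limit of quantification at baseline. Optional exploratory assays could also raise f, although the SAP does not say whether their results count.

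**The model already adjusts for treatment history.** This stands for the main effect. A reader might infer that genotype effects are confounded with treatment history outright. The narrower point is overlap between two interactions that are fitted in separate models.

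**Non-use of the historical genotype is not proven.** The SAP's amendment history refers to a Data Presentation Specification, which is not available here. What is established is that the SAP's stated rule gives the historical genotype no role.

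**Protocol-run assays with an explicit Unknown category are defensible.** This stands in part. Historical results come from mixed assays, and once added, their source will largely track treatment history. That is a reason to flag the source and keep an assay-only analysis. If exclusion is deliberate, the SAP should say so and give the reason.

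**The timing discrepancy is narrow.** This stands. SAP 7.6 also describes a baseline sample for sequencing, consistent with the protocol, whose schedule has sequencing samples at both screening and Day 1. Only the INNO-LiPA time differs: screening in SAP 2.4.1 and 7.6, Day 1 in the protocol schedule and footnote k. No effect on a result has been identified.

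**Conclusion.** The point holds as a weakness in a stated derivation rule. The omission follows from the text without any assumption. It is likely, but not shown, that Unknown is concentrated in the suppressed stratum. Across assumed typing rates of 0% to 80% there, Unknown runs from 60% down to 12% of the trial, given the 40% untreated aim is met and all untreated participants are typed. The arm-by-genotype interaction may then partly reflect treatment history.

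A reader might infer that the main results are affected. They are not: genotype enters neither the primary nor the key secondary tests, nor the multiple-imputation models. The effect is limited to exploratory subgroup, baseline and virology displays, and the planned Unknown category would make the gap visible. The change is worth making because the data are already collected and the rule is easy to state.

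**What to change.** In SAP 2.4.1, 4.2.2 and 7.6:

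1. Define analysis genotype as the INNO-LiPA or sequence result, stating which takes precedence when they disagree; otherwise the historical genotype recorded in the CRF; otherwise Unknown. State whether exploratory assay results count.
2. Tabulate genotype source and percentage Unknown by treatment-history stratum.
3. Keep the assay-only genotype analysis as a sensitivity analysis.
4. Reconcile the INNO-LiPA sample time with the protocol.

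The cost is SAP wording, one derivation from data already in the CRF, and one added table. The downside is small: historical genotypes come from mixed assays, and because their source will largely follow treatment history, the hierarchy reduces Unknown without fully separating genotype from treatment history. The source table and the assay-only analysis let the reader judge this.
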